2.4.2 Prior, concomitant and post therapies

Prior anti-neoplastic therapy

The number and percentage of subjects who received any prior anti-neoplastic medications will be summarized by treatment group. Prior anti-neoplastic medications will be summarized by setting (e.g. adjuvant, metastatic, etc.) and also by lowest ATC class, preferred term and treatment. Summaries will include total number of regimens, indication, reason for discontinuation of therapy and best response hematological. Listings will be produced for prior anti-neoplastic medications.

Anti-neoplastic medications will be coded using the WHO Drug Dictionary (WHO-DD). Details regarding MedDRA and WHO-DD version will be included in the footnote in the tables/listings.

The above analyses will be performed using the FAS.

Post treatment anti-neoplastic therapy

Anti-neoplastic therapies since discontinuation of study treatment will be listed and summarized by ATC class, preferred term, overall and by treatment group by means of frequency counts and percentages using FAS.

Concomitant medications

Concomitant therapy is defined as all interventions (therapeutic treatments and procedures) other than the study treatment administered to a subject coinciding with the study treatment period. Concomitant therapy includes medications (other than study drugs) starting on or after the start date of study treatment or medications starting prior to the start date of study treatment and continuing after the start date of study treatment.

Concomitant medications will be coded using the World Health Organization (WHO) Drug Reference Listing (DRL) dictionary that employs the WHO Anatomical Therapeutic Chemical (ATC) classification system and summarized by lowest ATC class and preferred term using frequency counts and percentages. Surgical and medical procedures will be coded using MedDRA and summarized by SOC and preferred term. These summaries will include:

1. Medications starting on or after the start of study treatment but no later than 30 days after start of last dose of study treatment and
2. Medications starting prior to start of study treatment and continuing after the start of study treatment.

All concomitant therapies will be listed. Any concomitant therapies starting and ending prior to the start of study treatment or starting more than 30 days after the last date of study treatment, or starting more than 30 days after the last date of study treatment and within the overall safety period will be flagged in the listing. The safety set will be used for all concomitant medication tables and listings.

2.5 Analysis of the primary objective

The primary objective of Part 1 of the study is to characterize the safety, tolerability, and the recommended Phase 2 dose (RP2D) of each combination partner used with ruxolitinib in subjects with myelofibrosis.

The primary objective of Parts 2 and 3 of the study is to evaluate the preliminary efficacy of the ruxolitinib combination treatments in subjects with myelofibrosis. Due to permanent enrollment halt, the Part 2 and Part 3 primary objective will not be pursued.

2.5.1 Primary endpoint

Part 1

The primary endpoint in Part 1 is the incidence of dose-limiting toxicities (DLTs) within the first two treatment cycles.

Part 2 and Part 3 (NOT applicable)

The primary endpoint in Parts 2 and 3 is the response rate (RR) at the end of Cycle 6.

The RR is the composite of anemia improvement and no spleen volume progression and no symptom worsening. For a subject to be considered a responder, all three components of the composite endpoint have to be fulfilled. The components of the composite endpoint are defined as follows:

- Anemia improvement is defined as an increase of hemoglobin from baseline of at least 1.5 g/dL. Anemia improvement requires absence of any PRBC transfusion in 12 weeks prior to achieving an increase of 1.5 g/dL. The increase in hemoglobin should be confirmed at least 2 weeks later.
- No spleen volume progression with progression defined as a spleen volume increase of 25% or more from baseline as measured by MRI/CT.
- No symptoms worsening as measured by the MSAF version 4 patient reported outcome (PRO). An increase in total symptom score (TSS) of 10 or more from baseline is considered worsening of symptoms.

2.5.2 Statistical hypothesis, model, and method of analysis**2.5.2.1 Part 1****Identification of a recommended dose for sitemartin and rinoterkib**

Identification of the recommended Phase 2 dose (RP2D) of the combination treatment will be based upon the estimation of the probability of dose-limiting toxicity (DLT) within the first two cycles for patients in the Dose-Determining Set (DDS). The maximum tolerated dose (MTD) is the highest drug dosage that is not expected to cause DLT in more than 33% of the treated subjects during the DLT evaluation period. The RP2D may be chosen prior to identification of the MTD and may be lower than the MTD. The decisions on new dose levels are made by the Investigators and Novartis study personnel in a dose escalation meeting based upon the review of patient tolerability and safety information (including the BLRM summaries of DLT risk) along with PK, PD and preliminary activity information available at the time of the decision.

The dose escalation will be guided by a Bayesian analysis of dose-limiting toxicity (DLT) data from Cycle 1 and Cycle 2. The relationship between dose and the probability of DLT is modelled using logistic regression. Details of the model are as follows.

Let $\pi(d)$ be the risk of DLT for the combination of ruxolitinib given at dose sitemartin dose d , the dose-DLT model is logistic:

Figure 2-1 Logistic DLT model.

$$\text{logit}(\pi(d)) = \log(\alpha) + \beta \log(d/d^*)$$

where d^* is used to scale the doses. Hence, $\alpha > 0$ is the odds of a DLT at d^* ; and $\beta > 0$ is the increase in the log-odds of a DLT by a unit increase in log-dose.

Assessment of patient risk

After each subject within each cohort is followed for two cycles, the BLRM will be updated and the posterior distribution for the risk of DLTs for patients at dose levels of sitemedrol will be evaluated. The posterior distributions will be summarized to provide the posterior probability that the risk of a DLT within the first two cycles lies within the following intervals (Table 2-6)::

Table 2-6 Toxicity levels

Under-dosing:	[0 , 0.16)
Targeted toxicity:	[0.16 , 0.33)
Excessive toxicity:	[0.33 , 1]

The escalation with overdose control (EWOC) principle

Dosing decisions are guided by the escalation with overdose control principle. A dose of sitemedrol may only be used for newly enrolled patients if the risk of excessive toxicity at that dose is less than 25%.

Prior distributions

A meta-analytic-predictive (MAP) approach was used to derive the prior distribution for the model parameters. The MAP prior for the logistic model parameters for this study is the conditional distribution of the parameters given the historical data (see [Neuenschwander et al 2014](#), [Neuenschwander et al 2010](#), [Spiegelhalter et al 2004](#)). MAP priors are derived from hierarchical models, which take into account possible differences between multiple historical studies.

A full description of the application of the MAP approach to derive the prior distributions of the model parameters is given in [Section 5.4](#).

Starting dose

The starting dose for sitemedrol in combination with ruxolitinib is 20 mg/day (day 1-5 each of a 28-day cycle). For this dose the prior risk of excessive toxicity is 15.42% (see [Section 5.4](#)), which satisfies the EWOC criterion. Any dose lower than 20 mg also fulfills the EWOC criterion. A full assessment of the prior risk of toxicity is given in [Section 5.4](#).

The starting dose for rinteqib in combination with ruxolitinib is 200 mg. For this dose the prior risk of excessive toxicity is 18.85% (see [Section 5.4](#)), which satisfies the EWOC criterion. Any dose lower than 200 mg also fulfills the EWOC criterion. A full assessment of the prior risk to patients is given in [Section 5.4](#).

Listing of DLTs

DLTs will be listed, and their incidence summarized by primary system organ class and worst grade (CTCAE version 5.0). Listings and summaries (if data warrant) will be based on the DDS.

DLT rate for crizanlizumab, sabatolimab and NIS793

For crizanlizumab, sabatolimab, and NIS793 the proposed RP2D is known prior to the study start and based on previous single agent phase I and phase II studies in solid and hematologic malignancies. A safety run-in is performed to assess the risk of unexpected toxicities and a dose escalation procedure is not followed for these combination treatments.

For each combination treatment, the DLT rate is determined as the observed number of patients in the DDS who experienced a DLT divided by the number of patients in the DDS.

Any DLTs occurring will be listed, and their incidence summarized by primary system organ class and worst grade (CTCAE version 5.0). Listings and summaries (if data warrant) will be based on the DDS.

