5.4.3.2 Single-agent siremadlin

For the MAP model for siremadlin, reference dose $d^* = 50$ mg is used, and data from one historical study with four regimens is available, so $S = 4$ is chosen.

Weakly informative normal priors are assumed for μ_1 and μ_2 , with means corresponding to a risk of DLT at the reference dose of 1/3, and a doubling in dose leading to a doubling in the odds of the risk of a DLT, respectively. Priors for τ_1 and τ_2 are assigned such that (1) their medians correspond to substantial between trial heterogeneity, and (2) their uncertainty (95% prior interval) cover plausible between-trial standard deviations ([Neuenschwander et al 2014](#)).

The prior distributions for the model used for deriving the MAP priors are specified in [Table 5-3](#).

Table 5-3 Prior distributions for the parameters of the MAP model used to derive the prior for the single-agent model parameters

Parameter	Prior Distribution
μ_1	N (mean = logit (1/3), sd = 2)
μ_2	N (mean = 0, sd = 1)
τ_1	log-normal (mean = log (0.5), sd = log (2)/1.96)
τ_2	log-normal (mean = log (0.25), sd = log (2)/1.96)
ρ	uniform (-1,1)

Historical data from study HDM201X2101

The prior is determined based on solid tumor data from study HDM201X2101.

In this study, four different regimens and dose-schedules were studied:

- 1A: dose on day 1 of a three week cycle
- 1B: dose on day 1 and on day 8 of a four week cycle
- 2A: once dose daily for the first two weeks of a four week cycle
- 2C: once daily dosing for the first week of a four week cycle

The doses in the different regimens are scaled to fit the schedule of siremadlin in the combination study, which is once daily for the first five days in a four-week cycle.

In study HDM201X2101, the original interest was in DLTs in cycle 1, however after observing cumulative toxicity DLTs within the first two cycles were considered for the recommended dose for expansion (document release date 28-Oct-2016). As the ruxolitinib combination study focuses on DLTs occurring in the first two cycles, the corresponding DLTs from the study HDM201X2101 were considered. When building the MAP prior distribution for siremadlin, the different regimens from study HDM201X2101 were considered as different studies (see Table 5-4).

Table 5-4 Regimens and doses from study HDM201X2101

Regimen	Dose level	Dose per cycle	Dose per day in 5 day schedule	N	DLTs (CYCLE 1)	Hematologic DLTs (CYCLE 2)	DLTs considered for MAP
1A	12.5	12.5	2.5	1	0	0	0
	25	25	5.0	1	0	0	0

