5.4.3.3 Summary of prior distributions

To obtain the MAP prior for $(\log(\alpha), \log(\beta))$, the predictive distribution obtained from data in [Table 5-4](#) will be mixed with a vague prior assuming a weight of 0.5. This mixing takes into account the fact the that patient population from study HDM201X2101 and this combination study are not identical and that in this combination study a single-agent model is used to account for both the effect of sitemedlin and potential interaction with ruxolitinib.

The MAP prior for $(\log(\alpha), \log(\beta))$ is a mixture of three multivariate normal distributions and it is summarized in [Table 5-5](#).

Table 5-5 Prior distribution for the model parameters

Prior for $(\log(\alpha), \log(\beta))$ in the single agent DLT-model for the combination of sitemedlin and ruxolitinib				
	Mean	Standard Deviations	Correlation	Weight
MAP component 1	(-0.771, 0.492)	(0.700, 0.435)	0.221	0.3255
MAP component 2	(-0.884, 0.051)	(0.573, 0.643)	0.237	0.1745

Prior for $(\log(\alpha), \log(\beta))$ in the single agent DLT-model for the combination of sitemadlin and ruxolitinib				
	Mean	Standard Deviations	Correlation	Weight
MAP component 3	(logit(1/2), 0)	(2, 1)	0	0.5

Prior summaries for DLT rates for are summarized in [Table 5-6](#).

Table 5-6 Summary of prior distribution of DLT rates for the combination of sitemadlin and ruxolitinib

Sitemadlin Dose (mg)	Prior Probabilities that P(DLT) is in the interval:			Mean	SD	Quantiles		
	(0, 0.16)	(0.16, 0.33)	[0.33,1]			2.5%	50%	97.5%
10	0.7982	0.0967	0.1051	0.1191	0.1895	0.0001	0.0443	0.7679
20	0.6526	0.1932	0.1542	0.1793	0.2103	0.0011	0.1046	0.8384
30	0.4687	0.3077	0.2235	0.2392	0.2217	0.0050	0.1713	0.8792
40	0.3035	0.3630	0.3335	0.2996	0.2297	0.0110	0.2425	0.9087

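### SAP Table 5-5 centres the vague half of the siremadlin BLRM prior at logit(1/2); the protocol has logit(1/3), and only logit(1/3) reproduces the figures printed in both documents

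*SAP*

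**What the plan says.** SAP Section 2.5.2.1 models DLT risk as logit(pi(d)) = log(alpha) + beta log(d/d*). Section 5.4.3.2 sets the scale: "reference dose $d^* = 50$ mg is used". Table 2-6 defines excessive toxicity as a DLT rate of 0.33 or more. A dose may be given to new patients only "if the risk of excessive toxicity at that dose is less than 25" per cent. For the 20 mg start the SAP reports: "For this dose the prior risk of excessive toxicity is 15.42" per cent.

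Section 5.4.3.3 describes the prior. The predictive distribution from the historical study "will be mixed with a vague prior assuming a weight of 0.5". The result "is a mixture of three multivariate normal distributions and it is summarized in" Table 5-5. Component 3, the vague one, has mean (logit(1/2), 0), SDs (2, 1), correlation 0 and weight 0.5.

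Protocol Table 16-5 (Section 16.6.3.2) gives the same three components, except that component 3 has mean (logit(1/3), 0). The prior summaries (SAP Table 5-6, Protocol Table 16-6) and the escalation scenarios (SAP Table 5-11, Protocol Table 16-11) carry identical numbers in the two documents. SAP Section 4 declares no change from the protocol-specified analysis.

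**The concern.** One set of printed outputs cannot come from two different priors. The disputed entry carries half the prior weight and sets where the vague component is centred at the 50 mg reference dose: a median DLT rate of 1/2 in the SAP, 1/3 in the protocol. Moving it upward raises the estimated overdose risk at every dose.

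The Part 1 objective, DLT incidence and the RP2D, is the primary objective that survives the enrollment halt, and SAP Section 2.5.2.1 is not marked as not applicable. Section 5.4 is offered there as the full account of the prior. An analyst or validating programmer who codes from Table 5-5 as it stands would obtain results that match neither the SAP's own tables nor the protocol.

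**Working it through.** **Inputs.** d* = 50 mg (SAP 5.4.3.2); cut-off 0.33 (SAP Table 2-6); limit 0.25 (SAP 2.5.2.1); components for (log alpha, log beta) from SAP Table 5-5 and Protocol Table 16-5:

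| Component | Mean | SD | Corr. | Weight |
|---|---|---|---|---|
| 1 | (-0.771, 0.492) | (0.700, 0.435) | 0.221 | 0.3255 |
| 2 | (-0.884, 0.051) | (0.573, 0.643) | 0.237 | 0.1745 |
| 3, SAP | (logit(1/2), 0) = (0, 0) | (2, 1) | 0 | 0.5 |
| 3, protocol | (logit(1/3), 0) = (-0.693, 0) | (2, 1) | 0 | 0.5 |

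**Formula.** For a component with means (m1, m2), SDs (s1, s2) and correlation r, write y for log beta. Then P(pi(d) >= 0.33) is the average over y ~ N(m2, s2) of

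Phi{ [m1 + r s1 (y - m2)/s2 + exp(y) log(d/50) - logit(0.33)] / [s1 sqrt(1 - r^2)] },

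with logit(0.33) = -0.708. The prior risk is the weighted sum over components.

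**20 mg, step by step** (log(20/50) = -0.916). Component 1 gives 0.0187 and component 2 gives 0.0311. Component 3 gives 0.2899 when centred at logit(1/3) and 0.4029 when centred at logit(1/2).

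- Protocol entry: 0.3255 x 0.0187 + 0.1745 x 0.0311 + 0.5 x 0.2899 = 0.0061 + 0.0054 + 0.1450 = 0.1565. The printed figure is 0.1542, so this reproduces to about 0.002.
- SAP entry: 0.0061 + 0.0054 + 0.5 x 0.4029 = 0.0061 + 0.0054 + 0.2015 = 0.2130. This does not reproduce.

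**Prior P(excessive toxicity), all doses**

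| Dose | Printed | logit(1/3) | logit(1/2) |
|---|---|---|---|
| 10 mg | 0.1051 | 0.1061 | 0.1518 |
| 20 mg | 0.1542 | 0.1565 | 0.2130 |
| 30 mg | 0.2235 | 0.2257 | 0.2891 |
| 40 mg | 0.3335 | 0.3340 | 0.4014 |

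Prior mean DLT rates tell the same story. Printed: 0.1191, 0.1793, 0.2392, 0.2996. With logit(1/3): 0.1196, 0.1800, 0.2400, 0.3005. With logit(1/2): 0.1529, 0.2208, 0.2861, 0.3503.

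**Scenarios.** The prior was multiplied by the likelihood pi(20)^r (1 - pi(20))^(n - r) on a two-dimensional grid and renormalised. Scenarios 1 to 7 were confirmed by importance sampling with 6 million draws. Values are P(excessive toxicity) at the dose listed.

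| Scenario | DLTs/n at 20 mg | Dose listed | Printed | logit(1/3) | logit(1/2) |
|---|---|---|---|---|---|
| 1 | 0/6 | 40 mg | 0.122 | 0.1203 | 0.1456 |
| 2 | 1/6 | 30 mg | 0.148 | 0.1519 | 0.1733 |
| 3 | 2/6 | 20 mg | 0.219 | 0.2215 | 0.2523 |
| 4 | 2/9 | 30 mg | 0.222 | 0.2258 | 0.2505 |
| 5 | 2/10 | 30 mg | 0.183 | 0.1891 | 0.2108 |
| 6 | 2/11 | 30 mg | 0.159 | 0.1591 | 0.1782 |
| 7 | 3/9 | 20 mg | 0.247 | 0.2470 | 0.2755 |
| 8 | 2/2 | 10 mg | 0.696 | 0.6980 | 0.7639 |
| 9 | 2/3 | 10 mg | 0.435 | 0.4343 | 0.4934 |

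With logit(1/3) the largest gap from print is about 0.006 (scenario 5).

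**Sensitivity to the cut-off.** Using 1/3 instead of the documented 0.33, 20 mg gives 0.1548 under logit(1/3) and 0.2111 under logit(1/2), so the cut-off does not explain the gap. Under logit(1/2), 30 mg a priori (0.2860) and scenario 7 (0.2690) stay above 0.25. Scenarios 3 (0.2472) and 4 (0.2438) fall below it.

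**The case against.** The strongest reply is that the point rests on one digit in one appendix cell. The machine-readable SAP text misspells several drug names, including siremadlin in Table 5-5 itself, so the 2 could be a misread 3. This stands as a condition: if the original PDF shows logit(1/3), the point falls away. Against it, the other numerals of Tables 5-5, 5-6 and 5-11 agree with the protocol.

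The neighbouring text on the MAP hyper-prior, "with means corresponding to a risk of DLT at the reference dose of 1/3", is context but not proof, because the vague component need not share the hyper-prior's centre. For rineterkib the two differ: logit(0.1) and logit(1/4). The recomputation is what identifies the wrong entry.

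A reader might infer three stronger things, and the documents do not support them.

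- *That the 15.42% is wrong or that the starting dose breaches the overdose limit.* The figure agrees with the protocol and its prior, and 21.3% would still be below 25%.
- *That scenarios 3 and 4 clearly change.* They exceed 0.25 by 0.0023 and 0.0005, while the same method differs from print by 0.0025 and 0.0038 for those scenarios under logit(1/3). They sit at the limit and no more can be said.
- *That actual dose decisions were affected.* The scenarios are hypothetical, and no document shows that any code used logit(1/2). Recruitment stopped on 17-Jun-2022, before both SAP amendments (30-Nov-2022 and 2-Jul-2024). Dose decisions also drew on tolerability, PK, PD and activity data alongside the model.

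**Conclusion.** The inconsistency holds on the text as it stands. SAP Table 5-5 contradicts Protocol Table 16-5 and the SAP's own Tables 5-6 and 5-11, and the Table 5-5 cell is the item that does not fit. Taken literally, it would raise the prior overdose risk at 20 mg by about 6 percentage points (21.3% against 15.42%) without crossing the limit. The clear crossings of 25% are 30 mg a priori (28.9%, printed 22.4%) and hypothetical scenario 7 (about 27.5%, printed 24.7%).

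The consequence is confined to the correctness and reproducibility of the reported Part 1 BLRM and RP2D analysis. The conclusion assumes that the printed digit is what the SAP really contains, and that the model, reference dose and 0.33 cut-off are as documented.

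**What to change.** Check component 3 of SAP Table 5-5 in the original PDF. If it reads logit(1/2), restate it as (logit(1/3), 0), so that it agrees with Protocol Table 16-5 and with SAP Tables 5-6 and 5-11. Leave the 15.42% sentence unchanged.

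Confirm that the BLRM code behind the reported Part 1 DLT and RP2D analysis uses logit(1/3). A rerun is needed only if that check finds logit(1/2). The cost is one table cell and one code check.

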2.5.2.2 Part 2 (NOT applicable)

No formal hypothesis testing or between arm comparison will be conducted in Part 2. The objective of this part of the study is to explore the disease-modifying activity of the combination treatments, and to drop the arm(s) that lack promising activity.

The arms that advance into Part 3 will be selected based on the totality of the data. That includes, among other data, efficacy, safety, PK/PD, [REDACTED] data as appropriate, and also data from the ruxolitinib single agent arm.

To determine whether a combination treatment has the potential to be disease-modifying and, as such, be eligible to advance into Part 3, the combination must not cross a specified futility boundary defined for the response rate with respect to the primary composite endpoint.

A combination treatment arm that shows an early sign of outstanding efficacy by crossing a specific efficacy boundary (i.e. when at least 10 subjects of a combination treatment are evaluable) at the first interim look may expand into Part 3 seamlessly, without stopping at the second interim look.

At the second interim look, the combination treatment arm must not cross a specified futility boundary (i.e. when at least 25 subjects of a combination treatment are evaluable) defined for the RR with respect to the primary composite endpoint.

The threshold for the first interim look is shown in Table 2-7

Table 2-7 1st interim look (seamless expansion to Part 3) efficacy threshold

Decision rule	Action
$P(RR > 0.3 D) > 80\%$	Preliminary efficacy declared

According to the first interim threshold, an arm is considered of clinical interest and will be advanced to Part 3 expansion if the posterior probability of the RR for the primary composite endpoint being greater than 0.3 is more than 80%. This first interim decision rule was determined such that arms with outstanding efficacy that warrant further development (i.e. True RR > 50%) will be advanced with higher probability, see [Section 3.1.2](#) for details.

Concerning the posterior probability of the response rate, let i index the study arm, let p_i be the corresponding responder rate with respect to the primary endpoint, let n_i be the number of

subjects of arm i , and let r_i be the number of responders in arm i . The number of responders r_i in arm i is modelled by a binomial distribution with parameters n_i and p_i . With the assumptions of a vague prior, $beta(1/2, 1/2)$, the posterior probability distribution of p_i is given by

$$p_i | n_i, r_i \sim beta\left(\frac{1}{2} + r_i, \frac{1}{2} + n_i - r_i\right)$$

For a given sample size n_i , the first interim threshold shown in [Table 2-7](#) can be transformed into a number of responders with respect to the primary endpoints for which preliminary efficacy would be declared, as shown in Table 2-8.

Table 2-8 1st Interim look efficacy regions for a given sample size

n_i	Region
9	≥ 4
10	≥ 5
11	≥ 5
12	≥ 5

The futility threshold of the 2nd interim look is shown in Table 2-9.

Table 2-9 Futility threshold

Decision rule	Action
$P(RR \leq 0.2 \text{Data}) > 50\%$	Declare combination arm futile

According to the futility threshold, an arm is dropped for futility if the posterior distribution of the response rate for the primary composite endpoint is less than or equal to 0.2 with a probability of more than 50%. This futility decision rule was determined such that arms with a response rate which are not of interest for further development, that are response rates of 10% or less, are likely to cross the futility threshold and would therefore be dropped at the end of Part 2, see [Section 3.1.2](#) for details.

For a given sample size n_i , the futility threshold shown in [Table 2-9](#) can be transformed into a number of responders with respect to the primary endpoints for which futility would be declared, see [Table 2-10](#).

Table 2-10 Futility regions for a given sample size

n_i	Futility region
24	≤ 4
25	≤ 4
26	≤ 5
27	≤ 5

Due to the discrete nature of the binomial distribution, the futility region does not necessarily change in the sample size n_i .

The response rate (RR) as defined in [Section 2.5.2.1](#) will be summarized using descriptive statistics (N, %) by treatment arm along with a 95% credible interval of the RR posterior

distribution. In addition, the probability that RR is less than or equal to 0.2 will be derived from the posterior distribution of RR.

